- patients with a follow-up period of less than one month. This occurs when a patient dies within the same month of registering with a general practice within the CCG. A limitation of the derived data from the patient registration data available to the IAU is that it only allows us to determine the month within which a move or a death occurred (see section on Data derived from NHAIS, p.18). In these cases, both dates are set as the day of the extraction date on which the new address or death was recorded

- patients without a record of prior emergency or elective admission in the three-year pre-study period (defined in section on Pre-period, p.24). These will be excluded because prior hospital data are required to define baseline patient characteristics, in particular patient comorbidities
- patients referred to an ICT between mid-May and mid-June 2017.

The exclusion criterion relating to no prior admissions is likely to exclude some patients who were referred to the ICT. An analysis done by NEHF CCG found that 20% of patients referred to the ICTs by end of February 2017 had no admissions (emergency or elective) in the previous two years. By allowing a period of three years, it is hoped that the number of exclusions will be minimised, while not unduly identifying historic comorbidities that have since been resolved (see section on Pre-period, p. 24).

Patients who change general practice within the CCG will be considered to be assigned to the locality of the general practice at the start of the follow-up period. NEHF CCG has confirmed that there were only a few cases where patients who were referred to one ICT changed general practice and ICT team.

The intervention group will be identified using the pseudonymised list of patients referred to an ICT, supplied by NEHF CCG (see sections on Data from NEHF CCG (p. 19) and Exposure variable (p. 23). Patients referred to an ICT after the mid-May cut-off and before mid-June will be excluded from the intervention group as they will not have a follow-up period of at least one month. They will also be excluded from the potential control group, as they would have received the intervention within the study period. Any patients referred to ICTs after mid-June 2017 may be considered as potential controls for this study.

Sources of data

Secondary Uses Services national administrative data

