The IAU will have access to pseudonymised (i.e. anonymised in line with the Information Commissioner's Office code of practice on anonymisation) SUS national administrative data, provided by the National Commissioning Data Repository (NCDR). SUS is a comprehensive repository for secondary health care data in England that is paid for by the NHS. It is used to support the NHS in the delivery of health care services and to trigger reimbursement for secondary care activity.

The IAU will create the analysis data set using SUS data for the period 1 July 2012 to 30 June 2017. This period will cover the study period up to the latest point for which it will have access to reliable data, as well as three years before the study period start date, which is data needed for measuring study covariates. SUS data for recent months may be incomplete as they will not include patients who have not yet been discharged. The IAU believes that data to June 2017 will be of sufficiently good quality, but we will check that the quality of the data is similar to earlier months and if necessary shorten the follow-up period.

Data derived from National Health Applications and Infrastructure Services

In addition, the NCDR holds monthly extracts from National Health Applications and Infrastructure Services (NHAIS) from August 2014 up to a month before the date of the data transfer to the IAU. These monthly extracts, created on the first Sunday after the 13th day of the month, contain demographic information about all registrations with general practices in

England, including date of birth, full residential address and the general practice at which the patient is registered. The date of death is also recorded in NHAIS for patients who died from August 2014 to the last available data extract.

Data derived by the NCDR based on these monthly extracts will enable the IAU to identify patients registered with a general practice in NEHF and the period within which they were registered there. This is done by analysing the history of registration information in NHAIS and identifying in which extract the recorded general practice changed. In addition, each patient's locality can be determined from their general practice code. Furthermore, the NCDR can identify those patients living in nursing or residential care homes, by matching the address information available in NHAIS with care home addresses available from the Care Quality Commission website.

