As recipient data controllers, NEHF CCG/NHS England can use their powers of disclosure under the Health and Social Care Act 2012 to share data to support IAU evaluations. To facilitate this, it may be necessary for the CCG local data to be transferred securely from the Data Services for Commissioners Regional Office (DSCRO) providing services to the CCG to NHS England's DSCRO (Arden and Great East Midlands) to enable it to be de-identified and linked to NHS England's national SUS data and/or other data as required to support the evaluation. The linked data will then be anonymised further (i.e. different pseudonyms applied) to mitigate the risk of re-identification when the data are made available to analysts in the IAU who will be undertaking the evaluation.ⁱⁱ

Study endpoints

Primary outcomes

The primary outcomes to be examined by the study are:

- number of **emergency admissions** per patient over the follow-up period
- number of **chronic ACS emergency admissions** per patient over the follow-up period
- number of **emergency admissions for urgent care sensitive conditions**
- the number of **A&E attendances** per patient over the follow-up period
- **average length of stay following an emergency admission** per patient.

All count endpoints will be modelled allowing for varying study lengths, by including an offset for amount of time at risk in the statistical analysis. The length of the follow-up period for each patient will vary between 1 and 23 months, depending on the date on which they entered the study (e.g. when during the study period they were referred to an ICT) and if they died or moved away during the study period (i.e. whether their time in the study was curtailed) (see section on Index dates and follow-up period, p. 23).

Emergency admissions are defined as separate hospital spells that either occur through the emergency room or as a result of direct, urgent referrals from a GP or other professional. Many emergency admissions are not avoidable with good care; therefore, evaluating ACS admissions may be a more appropriate outcome when evaluating a health care intervention.

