Proportion of deaths in hospital will be used as a proxy for patients dying in their preferred place of death. While patients may not die in their preferred place outside of hospital, it is assumed for the purposes of this analysis that locations outside of hospital (e.g. home, care home, hospice) would always be preferred over dying in hospital. Proportion of deaths is calculated by combining information on hospital deaths from the SUS data with information on all deaths from the NHAIS data.

Delayed transfers of care will not be evaluated, as the IAU does not have access to reliable data.

Variable definitions

Bedding-in period and study period

The ICTs were launched on 27 July 2015 across all five NEHF localities. Although the ICTs developed their capacity and services at different rates across the five localities, they were running services immediately. This study will not include a bedding-in period (i.e. a period omitted from the analysis to allow time for the interventions to become established). Although the earliest start date for the intervention group is 27 July 2015, the study period will start in mid-July 2015 (the exact date being the date of the NHAIS monthly extraction) to allow for potential control patients to be included from that date.

The study period will end mid-June 2017 (the exact date being the date of the NHAIS monthly extraction). During this period, most of the patients referred to ICTs were selected based on clinical judgement.

Exposure variable

A person is considered to be in the intervention group (i.e. exposed to the intervention) if they were registered with a NEHF general practice and referred to an ICT between 27 July 2015 and mid-May 2017. By only including patients referred up to mid-May 2017, the IAU allows for at least one month of exposure to the intervention. Persons in the intervention group will be identified from the list of referred patients, supplied in pseudonymised form from NEHF CSU.

Index dates and follow-up period

Each patient will be followed up within the study period for a length of time specific to that patient. A patient's follow-up period will start from the index date, which is defined as:

- If the patient was referred to the ICT, then the date of their first referral. For the purpose of this analysis, this is the date at which they are considered to have started the intervention.

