- If the patient was not referred to the ICT (i.e. in the potential control group), then monthly potential index dates will be assigned, starting from the latest of the following:
 - the study period start date (see section on Bedding-in period and study period, p. 23)
 - date of earliest registration with a general practice in NEHF CCG, set as the date of the extraction in which they are first known to have been registered with a general practice in NEHF.

If a patient was referred more than once, only the first date is used, that is, if patients were discharged and then subsequently referred again, they are treated as though they stayed on the ICT register. No differentiation will be made between active or dormant patients (see section on Integrated care teams, p. 12).

For potential control patients, monthly index dates will be assigned from mid-July 2015 up to mid-May 2017. As the first and last monthly dates may be based on extraction dates (see

above and below), the dates set for all other months will for consistency also correspond to the extraction date of the corresponding month. This will also enable more accurate information on whether a patient was a care home resident at the index date, which is one of the potential covariates (see section on Baseline variables, p. 25).

A person's follow-up period ends when the person either dies, moves from NEHF CCG or the study period ends. Thus, the end date is defined as the earliest of the following dates:

- the end of the study period, that is mid-June 2017, set to the date of the last available NHAIS extract
- date of death, set to the date of the extraction in which death is first recorded
- date of de-registration from CCG general practice, set to the day before the date of the extraction in which they were first registered with a general practice outside NEHF.

A person's follow-up period may therefore be between approximately 1 and 23 months.

The date of death is estimated as the extraction date of when they were first recorded as having died. However, as the true death date could be as early as the day after the previous extraction date, there is a risk that the follow-up period is overestimated by up to a month, during which time the patient would have no recorded hospital activity. However, as it is unlikely that the day of the month that a person dies is other than random, this is unlikely to introduce bias between the intervention and control groups.

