One of the main threats to the validity of this study is unobserved confounding. That is, although the IAU anticipates that the intervention and matched control groups will be similar in terms of observed variables (such as age and prior number of hospital admissions), there may be systematic differences between these groups that we do not observe, for example characteristics that informed clinical judgement to refer to ICTs. There is always a risk of unobserved confounding in non-randomised studies, but here the risk is larger due to patients being selected for the ICTs primarily based on clinical input from GPs or other health professionals.¹⁰ The lack of information on the subjective reasons for referring patients, together with a lack of primary care and community data, makes it difficult for us to identify what characteristics the referred patients were selected on and therefore to identify a matched control group that is similar to the intervention group in these characteristics.

Although there is no definitive way to assess the effect of unobserved confounding, it is possible to compare the rates of the intervention and matched control groups on an endpoint unrelated to the intervention.⁴⁷ On the assumption that the intervention is unlikely to have had a large positive or negative impact on overall mortality within the follow-up period, then differences in mortality rates would make us doubt the performance of the matching. For example, if enrolled patients died at a higher rate than matched control patients, this might suggest that they were in worse health than controls at the point of enrolment.⁴⁸ However, there is also a possibility that good care may result in prolonged life and therefore less deaths during our follow-up period. The IAU will therefore compare the rates of all-cause mortality over the study period. The IAU will also perform a survival analysis using Kaplan-Meier estimates, censoring patients who moved or reached the end of the study period. Similar mortality and survival rates will be indicative of balanced groups, while differences would need to be interpreted with caution.

If there is found to be a difference in mortality between the intervention and control groups, the IAU will explore possible reasons for the imbalance and if possible consider subsetting the cohort in such a way as to remove any bias.

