There may also be positive unintended consequences of the ICTs on the comparator group, for example if communication and relationships across organisational boundaries improves as a result of staff participation in the ICTs.

Statistical conclusion validity

The IAU is expecting a sample size of approximately 900 patients. This may be too small a sample size to identify a significant effect at conventional 95% significance levels if the effect is small or there is large variability within the groups.

A recent evidence review suggested that initiatives aiming to better manage patients 'at risk' are often highly valued by patients but seldom reduce hospital activity.¹⁸ There are several contributing factors, including limitations of risk stratification tools to identify patients before they deteriorate and that these initiatives often identify unmet need and provide more timely access to care.¹⁸ A limitation of our study is that the IAU cannot distinguish between additional hospital activity that is due to good and timely care and other hospital activity. However, by evaluating the number of ACS hospital admissions, we may be able to identify any reductions in emergency admissions due to good quality primary and community care.

Construct validity

The success of an ICT is in both correctly identifying patients who would benefit from additional help and in the care they receive. This evaluation takes into account the effect of the ICTs on the patients referred to them and not the effect of the patient selection process (i.e. identifying patients most at risk who may benefit from the ICT).

SUS data is an administrative database and has not been subjected to the cleaning rules that the Hospital Episode Statistics database is. However, the IAU Data Management team will perform data checks and cleaning.

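### The one-month minimum follow-up rule selects on survival after the index date, and does so differently in ICT and control patients, by an amount and in a direction that depend on an undefined month

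*Protocol*

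**What the plan says.** The exclusion list under Study cohorts (Definition of study cohort) removes "patients with a follow-up period of less than one month. This occurs when a patient dies within the same month of registering" with a practice in the CCG, and adds that both dates are then the same extract date.

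Index dates and follow-up period sets the start of follow-up differently by group. For ICT patients: "If the patient was referred to the ICT, then the date of their first referral". For potential controls it is a monthly extract date: "the dates set for all other months will for consistency also correspond to the extraction date of the corresponding month". Death ends follow-up in both groups in the same way: "date of death, set to the date of the extraction in which death is first recorded". Extracts are "created on the first Sunday after the 13th day of the month" (Sources of data).

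Primary outcomes states the result: "The length of the follow-up period for each patient will vary between 1 and 23 months", and lists death and moving away among the reasons for the variation. Sensitivity analyses uses all-cause mortality and Kaplan-Meier survival to look for unobserved confounding: "differences in mortality rates would make us doubt the performance of the matching". The July 2018 Addendum adds exclusions to the cohort definition and leaves this one unchanged.

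**The concern.** The operative words of the exclusion concern length of follow-up. The explanation attached to them covers only death in the month of GP registration. For an ICT patient the index date is a referral that can fall on any day, so a death or departure before the next extract also gives less than one extract interval of follow-up. A control who dies the day after index is credited with the whole interval.

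The rule therefore conditions on something that happens after the index date, and the condition is not the same in the two groups. What is at stake is mainly the mortality check. The Protocol reads higher ICT mortality as a possible sign that ICT patients were sicker at enrolment, and similar mortality as a sign of balance. If early ICT deaths alone are deleted, a sicker ICT group can look balanced. The Background describes ICT patients as including people near the end of life, so some early deaths are to be expected.

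**Working it through.** **Inputs from the Protocol.** Extract calendar, index-date rules, death-date rule and the exclusion, as above; referrals from 27 July 2015 to mid-May 2017; "The IAU is expecting a sample size of approximately 900 patients", matched 1:1. **Assumptions** (the Protocol gives no mortality rate): 30-day mortality of 1%, 2% or 4%, constant hazard, the same in both groups; referral days uniform; each control indexed on the extract at or just before the matched referral.

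**The Protocol's own figure.** Taking the first Sunday after the 13th of each month gives extracts from 19 July 2015 to 18 June 2017: 23 intervals, 15 of 28 days and 8 of 35 days. 15 × 28 + 8 × 35 = 700 days, and 700 / 30.44 = 23.0 months. The stated maximum of 23 months is reproduced.

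**Share of first-30-day ICT deaths removed.** Let R be the days from referral to the next extract.
- Month = one extract interval (death before the next extract is excluded). In a 28-day interval, R runs over 1 to 27 for referrals off the extract day: 378 / (28 × 30) = 0.45. In a 35-day interval, the sum of min(R, 30) over 1 to 34 is 585: 585 / (35 × 30) = 0.557. Of the 658 possible referral days, 412 lie in 28-day and 246 in 35-day intervals: 0.626 × 0.45 + 0.374 × 0.557 = 0.49.
- Month = 28 days. The 35-day term becomes 378 / (35 × 30) = 0.36: 0.626 × 0.45 + 0.374 × 0.36 = 0.42 (0.41 by day-by-day enumeration).

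**Controls.** Every control death in the first interval is credited with 28 or 35 days, so none is removed under either reading. With a 30- or 31-day month, all control deaths in a 28-day first interval are removed: 0.626 × 28/30 = 0.58 (0.61 if each interval counts equally, 15/23 × 28/30).

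**Day-by-day enumeration over all referral dates:**

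| Reading of one month | First-30-day deaths removed, ICT / control | ICT deaths removed per 900 at 1% / 2% / 4% | Control deaths removed per 900 | Mortality rate ratio at 2% (1.000 without the rule) |
|---|---|---|---|---|
| One extract interval | 49% / 0% | 4.4 / 8.8 / 17.7 | 0 | 0.954 |
| 28 days | 41% / 0% | 3.7 / 7.5 / 15.0 | 0 | 0.961 |
| 30 days | 47% / 58% | 4.3 / 8.5 / 17.1 | 5.3 / 10.5 / 21.1 | 1.009 |
| 31 days | 50% / 58% | 4.5 / 9.1 / 18.2 | 5.3 / 10.5 / 21.1 | 1.006 |
| Registration-month deaths only | 0% / 0% | 0 | 0 | 1.000 |

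If follow-up is compared with the length of the interval in which the referral falls, some deaths just after the next extract also fail, and the first row becomes 5.0 / 9.9 / 19.9. This gives the upper end of 4 to 20.

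The ratio of 1.000 without the rule agrees with the Protocol's view that rounding death dates does not by itself bias the comparison. The bias comes from combining the rounding with the exclusion.

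**Front-loaded deaths.** With an assumed annual hazard of 0.2 to 0.4, tripled in the first 30 days, the interval and 28-day readings give rate ratios of about 0.88 to 0.91 with uniform referrals, against 1.01 without the rule.

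**Admissions.** A simulation assuming 1.2 emergency admissions per year, rising to 10 per year near death, gave a rate ratio of 0.994 to 0.999 with the rule in force.

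**The case against.** The strongest reply is that the exclusion means only what its explanation says: registration and death on the same extract, hence zero follow-up. No sentence says that a death soon after referral is excluded, and for ICT patients the Protocol secures a month through the mid-May 2017 referral cut-off. On that reading there is no asymmetry. The reply shows that the text is ambiguous, but it does not remove the problem. The Protocol states a minimum follow-up of one month while naming death as a reason for curtailment, and that minimum is false for ICT patients if early deaths after referral are kept. Either the rule removes them or the stated minimum is wrong.

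A reader might go further and infer that the rule biases mortality and the death outcomes in favour of the ICTs. The Protocol does not support that. The month is not defined in days, 15 of the 23 intervals are 28 days long, and at 30 or 31 days more control than ICT deaths are removed. Place of death is conditional on dying, and nothing is said about where early deaths occur, so no direction can be given for it. Nor is it true that no control can be lost under the shorter readings: a mover's end date is the day before the extract, so a control who moves in a 28-day first interval has 27 days.

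Three mitigating points stand. The Protocol calls similar mortality only indicative of balance. It plans to compare follow-up length and reasons for leaving. It also requires a cohort flow diagram, which could make the exclusions visible.

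**Conclusion.** The point holds as a defect of definition with a modest consequence. As written, the rule selects on survival after the index date, and differently by group. Under an extract-interval or 28-day month it lowers the ICT mortality rate by about 4% to 5% relative at an assumed 30-day mortality of 1% to 4% with constant hazard, and by more if deaths are front-loaded. Under a 30- or 31-day month it moves the ratio by about 1% the other way.

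The shift is smaller than sampling error. The enumeration gives about 100 to 330 ICT deaths per 900, so with similar numbers of controls the standard error of the log ratio is √(2/100) = 0.14 to √(2/330) = 0.08. It is systematic, however, and under the shorter readings it pulls towards hiding sicker ICT patients in the one check aimed at that threat. Every size given here rests on assumed mortality. The primary admission outcomes are barely affected.

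**What to change.** Replace the exclusion with a rule on potential follow-up only: index date no later than the mid-May 2017 extract, in both groups. Keep every patient who dies or leaves after the index date and let the offset carry the short time. Exclude only records with zero follow-up because registration and death fall on the same extract. Correct the stated 1-to-23-month range to match.

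Do not fill in short follow-up from hospital discharge dates. These exist only for deaths in hospital, so time would be measured differently by place of death, which is itself an outcome.

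The Addendum shows that the analysis has been run. First state how the rule was applied and how many patients it removed in each group. If early deaths were dropped, rerun the mortality and Kaplan-Meier comparisons with them retained, and report place of death on the same cohort.

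The cost is a sentence or two of text and, at the assumed rates, some 4 to 20 ICT deaths restored per 900, plus any early leavers. Those restored must be matched, which is not trivial with about 750,000 potential control records, and a few patients with very short follow-up enter the models.

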National priority – Discharge to Assess and Trusted assessor models	Oct-16
One "ready for discharge" list for all agencies	Oct-16
Plan to close and monitor the 61-bed gap – simple discharges before 12:00	Oct-16
Home for Christmas – 5-week escalation and capacity plan to cover Christmas and New Year	Oct-16
Ensure all "frequent attender" patients have robust community management plans	Nov-16
IRIS at Frimley Park Hospital	Jan-17
Yateley urgent care centre	Feb-17
Aldershot & Farnborough locality plans Development and expansion of ICT capacity and services Development of rapid home visiting services via community paramedics	Mar-17
Farnborough community paramedics	Apr-17

Enhanced Recovery @ Home full service	Apr-17
Carers' Hub (Fleet)	Apr-17
Out of hours prescribing pharmacists	Apr-17
National priority – NHS 111 Increasing the number of calls transferred for clinical advice	Apr-17
Additional support to Care and Nursing homes	Apr-17
Farnborough Safe Haven (Oasis) – 6-month pilot	Apr-17
Farnham urgent care centre	Jun-17
Fleet locality Development and expansion of ICT capacity and services. Development of rapid home visiting services via community paramedics	Jun-17
Fleet Web GP pilot	Jul-17
Farnham Rapid Home Visiting Service	Jul-17
Farnham Dermatology Service	Aug-17
MISSION Clinics	Oct-17

Source: NEHF CCG and Happy, Healthy, at Home Vanguard

*Before Vanguard status

CHC: Continuing Healthcare.

Some activities were set up to benefit the broader population, for example changes to primary care; a social prescribing service; urgent care hubs; carers' hubs; and Recovery College courses.

Other activities will primarily benefit patients with complex needs, long-term conditions or who are older and frail, by providing more and appropriate care in the community, thereby improving their overall health, quality of life and reducing their secondary care needs. There are many interventions that may target this group of patients:

- **ICTs (the subject of this evaluation):** Patients with highest risk and need are referred to multidisciplinary teams who regularly meet, develop care plans and deliver joined-up care for these patients. As shown in the list of core aims (p. 9), this is one of the main interventions.

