In summary, the NCDR will derive and provide the following limited data from the NHAIS database, for patients registered with a NEHF general practice at any time during the period mid-July 2015 to mid-June 2017:

- patients' month and year of birth
- patients' month and year of death
- patients' general practice code
- patients' extract date when the general practice code changed
- flag if a patient is resident in a nursing or residential care home in NEHF at any time during the period and the date of the move into the care home.

The dates of death and registering with a practice will be estimated by using the date of the extraction.

It is believed that data to mid-June 2017 (i.e. the June 2017 extract) will be of sufficiently good quality, but the IAU will do comparisons of monthly data to check this and adjust the study period accordingly. The data derived from NHAIS will be linked to the SUS data via a pseudonymised patient identifier.

Data from NEHF CCG

The IAU will request the following information from NEHF CCG:

- pseudonymised patient IDs for patients who were referred to ICTs from 27 July 2015 to mid-June 2017
- date of referral
- the locality of the ICT to which they were referred.

Information on patient IDs and date of referral will allow the IAU to identify the intervention group and the start dates of their intervention. Although only patients referred up to mid-May will be included in the intervention group, data on patients referred until mid-June will be needed to ensure that subsequent referrals are excluded from the control group. Patients referred to an ICT after mid-June 2017 can serve as a control patient for the study period of this evaluation. Information on locality for referred patients will allow the IAU to check that the general practice codes from NHAIS can be used to derive locality correctly. This will

confirm whether matching within localities and doing subgroup analyses by locality are feasible.

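### Controls qualify only if not referred at any time up to mid-June 2017, so eligibility depends on events after the index date; the bias probably runs against the ICTs and its size is unknown

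*Protocol*

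**What the plan says.** The rule has to be assembled from three places in the Protocol's Methods.

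- *Index dates and follow-up period* defines a potential control by absence of referral, without tying this to a date: "If the patient was not referred to the ICT (i.e. in the potential control group), then monthly potential index dates will be assigned". For these patients "monthly index dates will be assigned from mid-July 2015 up to mid-May 2017". The Addendum later reduced this to one date per quarter for those under 65.
- *Definition of study cohort* deals with patients referred between mid-May and mid-June 2017, who are too late for the intervention group: "They will also be excluded from the potential control group, as they would have received the intervention within the study period". Only referral after the study ends leaves a patient eligible: "Any patients referred to ICTs after mid-June 2017 may be considered as potential controls for this study".
- *Sources of data* (Data from NEHF CCG) explains why referral records up to mid-June are requested: "data on patients referred until mid-June will be needed to ensure that subsequent referrals are excluded from the control group".

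Patients referred from 27 July 2015 to mid-May 2017 form the intervention group. A person's "follow-up period ends when the person either dies, moves from NEHF CCG or the study period ends", so a control's own referral is not an end point, and the "follow-up period may therefore be between approximately 1 and 23 months". On who is referred, the Background says: "Patients with highest risk and need are referred to multidisciplinary teams".

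**The concern.** A control given an index date in September 2015 qualifies only if nobody refers that person in the following 21 months. A patient referred in 2017 cannot serve as a not-yet-referred control in 2015 or 2016, even though the two were indistinguishable at that date. ICT patients face no comparable condition on what happens after their index date.

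If referral responds to rising need, the deleted controls are on average those whose hospital use went up. The control event rate then falls and the rate ratio (ICT over control) rises even if the ICTs do nothing.

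This differs from the unobserved confounding treated under *Sensitivity analyses* and *Limitations and sources of bias*, which concerns differences present at referral. Here the bias can arise even if referral depends only on measured history, because eligibility uses later information. Matching and regression on pre-period variables cannot repair that. Neither the limitations nor the Addendum mentions it.

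Emergency admissions and A&E attendances are primary outcomes, and the protocol itself expects that such initiatives seldom reduce hospital activity. A modest upward bias could therefore hide a modest benefit.

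**Working it through.** The document gives no figure for this bias, so there is nothing to reproduce. The size has to be bracketed.

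**Inputs from the Protocol**
- 1,051 patients referred by June 2017 (*Integrated care teams*).
- 225,000 registered people (*Background*) and a target of the top 2%: 0.02 × 225,000 = 4,500.
- About 750,000 potential control records (*Addendum*, Matching parameters), with at most 23 index dates per person: 750,000 / 23 = 32,609 people at least. The true number is higher, because under-65s had only quarterly dates.

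**Formula.** Among patients eligible at an index date, let a share q be referred later, and let their untreated event rate from that date be r times that of never-referred patients. If never-referred patients have rate λ, the not-yet-referred pool has rate λ[1 + q(r − 1)]. The never-referred rule therefore multiplies the rate ratio by 1 + q(r − 1).

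**Values of q**
- Whole pool: 1,051 / (1,051 + 32,609) = 3.1% at most.
- Pool of target size: 1,051 / 4,500 = 23%.

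The document does not give r, so it is assumed:

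| q | r = 0.8 | r = 1.5 | r = 2 | r = 3 |
|---|---|---|---|---|
| 3% | 0.994 | 1.015 | 1.03 | 1.06 |
| 23% | 0.954 | 1.115 | 1.23 | 1.46 |

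The direction reverses only if later-referred patients use hospital less than comparable never-referred ones (r < 1).

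**Null simulations (no ICT effect, assumed referral models)**

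*Referral driven only by measured 60-day and 12-month admission counts; matching on the 60-day, year −1 and year −2 counts; 12 replicates:*

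| Pool | Never-referred RR | Not-yet-referred RR | Plain censoring at referral, RR | Control time after referral |
|---|---|---|---|---|
| 4,500 | 1.354 | 0.989 | 1.229 | 27% |
| 12,000 | 1.196 | 1.010 | 1.162 | 12% |
| 35,000 | 1.071 | 0.998 | 1.040 | 3% |

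*Referral driven by latent current risk; 1,051 referrals over 23 months; matching on index month and on 2- and 12-month counts; 8 replicates per scenario.* Unobserved confounding is present here too, and the not-yet-referred RR is itself 1.26 to 1.66. The rule's own contribution is the ratio of never-referred to not-yet-referred RR: 1.00 to 1.06 with a pool of 33,000, and 1.10 to 1.34 with 4,500. Control mortality differed between the two rules by under 0.5 percentage points, in either direction. The planned mortality comparison may therefore not reveal the problem: a patient who dies early cannot be referred later and so stays in the pool.

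*Variants with and without deaths, rising referral volume and 30% of referrals unrelated to admissions; 6 replicates:* the same ratio was 0.97 to 1.05 with pools of 33,000 and 60,000 (replicate SD 0.04 to 0.10), and 1.26 to 1.49 with 4,500.

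**The case against.** The strongest reply concerns size. A reader might infer from the small-pool results that the study overstates hospital use in the ICT group by a third. The document does not support that. Under *Integrated care teams*, the top 2% is something the Vanguard hopes to reach over time, not the pool from which patients were referred. The Addendum's record count implies at least 32,600 people, where the simulated bias is small and partly within simulation noise. *Definition of study cohort* also reports that 20% of referred patients had no admission in the previous two years, so referral was not confined to the heaviest hospital users. This stands. It does not settle the matter, because controls are matched to resemble ICT patients and the relevant pool is a higher-risk subset whose size is not stated.

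The simulated referral models are also simple. Actual referral was mostly clinical judgement, sometimes perhaps for non-clinical reasons, and the planned matching and regression use many more variables. Both would weaken the link between later referral and residual risk, so the direction is likely rather than proven.

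Timing cuts both ways. Referrals came late (84 in January 2017; 166 more between the April and June 2017 totals of 885 and 1,051). With balance on index quarter, many controls need stay unreferred for only a few months, while early index dates lose most of the future referrals.

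Finally, following controls through their own referral puts treated time into the control arm and departs from the stated comparison with patients who were not referred. That is a fair reason not to discard the never-referred analysis.

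**Conclusion.** The point holds as a design flaw. The three sections together condition control eligibility on up to 23 months of post-index history. The sentence on the data request alone mainly covers the last month of referrals.

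The likely effect is to raise the admission and A&E rate ratios, provided later-referred patients have higher use than comparable never-referred ones. The size is about 0% to 7% if the comparable pool is near the whole control pool, and about 10% to 35% or more only if it is as small as 4,500. The truth probably lies between, and the document cannot place it.

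A reader might also infer that the results would be mistaken for harm. The protocol already says that even a significant result needs caution, so this goes too far. What is missing is recognition of this particular bias and an analysis that would show how much it matters.

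**What to change.** Add a second control pool: at each index date, every registered patient who meets the other criteria and has not been referred by that date. Re-match, and report the result alongside the never-referred analysis in two forms:

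1. Follow-up to death, move or study end regardless of later referral, with the share of control time after referral reported.
2. Follow-up censored at the control's own referral, with inverse-probability-of-censoring weights. Plain censoring is not enough (null rate ratio 1.04 to 1.23 above), and the weights can correct only for what the hospital data record about referral.

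State the bias and its likely direction under *Internal validity*. The Addendum describes analyses already done, so label the addition as post hoc.

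**Cost.** Referral dates are already requested and dated control records are already part of the design, but later-referred patients need control records too. The work is a changed eligibility filter plus another round of matching and modelling, which is not trivial with about 750,000 records. Post-referral control time dilutes any ICT effect in form 1 (3% to 27% of control time in the first simulation). Some patients will contribute to both groups, so variance estimates should be clustered by patient.
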